5.1.2 Transversus abdominis plane (TAP) Nerve Block

The transversus abdominis plane (TAP) nerve block is a peripheral nerve block that targets nerve roots T6 to L1, which innervate the anterior abdominal wall. The block is placed by administering local anesthetic into the fascial plane between the internal oblique muscle and the transversus abdominis muscle.^{1, 2} TAP nerve blocks have previously been shown to improve immediate post-operative patient comfort and reduce post-operative narcotic usage in a variety of other abdominal surgeries including abdominoplasty, laparotomy, and cesarean section.³⁻⁷

5.1.3 Bupivacaine (Bupivacaine Hydrochloride)

As reported on FDA-approved drug products website:

<http://www.accessdata.fda.gov/drugsatfda_docs/label/2015/018053s055lbl.pdf>

“The onset of action with Bupivacaine Hydrochloride is rapid and anesthesia is long lasting. The duration of anesthesia is significantly longer with Bupivacaine Hydrochloride than with any other commonly used local anesthetic. It has also been noted that there is a period of analgesia that persists after the return of sensation, during which time the need for strong analgesics is reduced. After injection of Bupivacaine Hydrochloride for caudal, epidural, or peripheral nerve block in man, peak levels of bupivacaine in the blood are reached in 30 to 45 minutes, followed by a decline to insignificant levels during the next three to six hours. The half-life of Bupivacaine Hydrochloride in adults is 2.7 hours.

Amide-type local anesthetics such as Bupivacaine Hydrochloride are metabolized primarily in the liver via conjugation with glucuronic acid. Patients with hepatic disease, especially those with severe hepatic disease, may be more susceptible to the potential toxicities of the amide-type local anesthetics. Pipecoloxyline is the major metabolite of Bupivacaine Hydrochloride. The kidney is the main excretory organ for most local anesthetics and their metabolites. Urinary excretion is affected by urinary perfusion and factors affecting urinary pH. Only 6% of bupivacaine is excreted unchanged in the urine.

When administered in recommended doses and concentrations, Bupivacaine Hydrochloride does not ordinarily produce irritation or tissue damage and does not cause methemoglobinemia.

Bupivacaine Hydrochloride is indicated for the production of local or regional anesthesia or analgesia for surgery, dental and oral surgery procedures, diagnostic and therapeutic procedures, and for obstetrical procedures.

Bupivacaine Hydrochloride is contraindicated in patients with a known hypersensitivity to it or to any local anesthetic agent of the amide-type or to other components of Bupivacaine Hydrochloride solutions.

Maximum dosage limit must be individualized in each case after evaluating the size and physical status of the patient, as well as the usual rate of systemic absorption from a particular injection site. Most experience to date is with single doses of Bupivacaine Hydrochloride up to 225 mg

with epinephrine 1:200,000 and 175 mg without epinephrine; more or less drug may be used depending on individualization of each case. These doses may be repeated up to once every three hours. In clinical studies to date, total daily doses have been up to 400 mg.⁸

5.2 Availability

InfuTronix, LLC, will be providing the Nimbus Ambulatory Infusion System sets, at no cost to Stanford Hospital.

5.3 Agent Ordering

InfuTronix, LLC agrees to provide the Institution, at no cost to the Institution, as many as two hundred (200) units of the Product complete with appropriate patient accessories along with the relevant Documentation. In addition, in order to enable Institution to implement the Product, InfuTronix, LLC agrees to: (i) conduct a site survey of the Institution's facilities; (ii) provide the Product; and (iii) remove the Product upon the expiration of this Agreement. Risk of loss for Institution's existing equipment shall at all times remain with Institution. InfuTronix, LLC also agrees to provide training for Institution's medical staff and technical staff on how to properly use the Product, to provide technical support for device failures or problems, and to provide technical updates as required for both the hardware and software components of the Product.

InfuTronix, LLC Contact Information:

[name]

Director of Sales and Business Development InfuTronix, LLC

5.4 Agent Accountability

The InfuTronix, LLC, Nimbus Ambulatory Infusion System products will be stored securely by the Department of Anesthesia. All stores of bupivacaine will be stored and dispensed by the Stanford Hospital Pharmacy, as is general protocol for all local anesthetics used for peri-operative analgesia.

6. DOSE MODIFICATIONS

Doses will be standardized across each patient group to the following, and no modifications shall be made:

- Initial bolus of 15mL pre-operatively
- 10mL bolus q4h intraoperatively with an option for 1-2mL per hour basal rate
- 10mL bolus q4h post-operatively with an option for 1-2mL per hour basal rate

The Intervention group will receive an infusion of 0.125% bupivacaine, while the Control/Placebo group will receive an infusion of normal saline.

7. ADVERSE EVENTS AND REPORTING PROCEDURES

7.1 Potential Adverse Events

As reported on FDA-approved drug products website:

<http://www.accessdata.fda.gov/drugsatfda_docs/label/2015/018053s0551bl.pdf>

“The most commonly encountered acute adverse experiences which demand immediate counter measures are related to the central nervous system and the cardiovascular system. These adverse experiences are generally dose related and due to high plasma levels which may result from over dosage, rapid absorption from the injection site, diminished tolerance, or from unintentional intravascular injection of the local anesthetic solution. In addition to systemic dose-related toxicity, unintentional subarachnoid injection of drug during the intended performance of caudal or lumbar epidural block or nerve blocks near the vertebral column (especially in the head and neck region) may result in underventilation or apnea (“Total or High Spinal”). Also, hypotension due to loss of sympathetic tone and respiratory paralysis or underventilation due to cephalad extension of the motor level of anesthesia may occur. This may lead to secondary cardiac arrest if untreated. Patients over 65 years, particularly those with hypertension, may be at increased risk for experiencing the hypotensive effects of Bupivacaine Hydrochloride. Factors influencing plasma protein binding, such as acidosis, systemic diseases which alter protein production, or competition of other drugs for protein binding sites, may diminish individual tolerance.”⁸

7.2 Adverse Event Reporting

Adverse events will be graded according to CTCAE v4.03. Both Serious and Non-Serious Adverse Events will be clearly noted in source documentation and listed on study specific Case Report Forms (CRFs). The Protocol Director (PD) or designee will assess each Adverse Event (AE) to determine whether it is unexpected according to the Informed Consent, Protocol Document, or Investigator’s Brochure, and related to the investigation. All Serious Adverse Events (SAEs) will be tracked until resolution, or until 30 after the last dose of the study treatment.

SAEs CTCAE Grade 3 and above, and all subsequent follow-up reports will be reported to the Stanford Cancer Institute Data and Safety Monitoring Committee (DSMC) using the study specific CRF regardless of the event’s relatedness to the investigation. Following review by the DSMC, events meeting the IRB definition of ‘Unanticipated Problem’ will be reported to the IRB using eProtocol within 10 working days of DSMC review, or within 5 working days for deaths or life-threatening experiences.

8. CORRELATIVE/SPECIAL STUDIES

There are no planned correlative studies.

9. STUDY CALENDAR

	Pre-Study	POD 0	POD 1	POD 2	POD 3-Discharge	1-6 months post-operatively
Investigational Treatment		X	X	X		
Informed consent	X					
Demographics	X					
Medical history	X					
Height	X					
Weight	X					
TAP catheter		X	X	X		
PCA		X	X	X		
Adverse event evaluation		X	X	X	X	
Evaluation for discharge ^a		X	X	X	X	
Pain evaluation	X	X	X	X	X	
BREAST-Q questionnaire	X					X

^aPatients will be evaluated daily for meeting discharge criteria and discharged when all criteria are met (detailed in Section 4.2.5).

10. MEASUREMENTS

For clinicaltrials.gov and Stanford Clinical Trials Directory compliance

Primary Outcome Measure: Total oral morphine equivalents of narcotic used in first 48 hours post-operatively after breast reconstruction.

- **Title:** Post-operative Narcotic Usage
- **Time Frame:** First 48 hours post-operatively.
- **Safety Issue:** No

Note: Each outcome measure listed within the protocol will necessitate legally required results reporting to clinicaltrials.gov within one year after the completion of the primary outcome measure.

10.1 Primary Outcome Measure: Post-operative Narcotic Usage

10.1.1 Measurement Definition

Post-operative Narcotic Usage will be measured in total oral morphine equivalents (OME) calculated by summing all narcotics used in the first 48 hours post-operatively.

10.1.2 Measurement Methods

Post-operative Narcotic Usage will be measured by review the patient's chart and medication administration history and totaling all narcotics administered.

10.1.3 Measurement Time Points

Post-operative Narcotic Usage will be measured in 8-hour time intervals (midnights to 8am, 8am to 4pm, 4pm to midnight) while the patient is hospitalized. The primary outcome will evaluate total narcotic usage in the first 48 hours post-operatively.

10.2 Secondary Outcome Measure: Post-operative Pain Score

10.2.1 Measurement Definition

Post-operative Pain Score is defined using Visual Analog Scale (VAS), a patient reported pain score on a scale of 0-10.

10.2.2 Measurement Methods

Post-operative Pain Score will be measured by asking patient to rate their pain on the VAS.

10.2.3 Measurement Time Points

Post-operative Pain Score will be measured every 4 hours post-operatively unless the patient is sleeping.

10.3 Secondary Outcome Measure: Post-operative Anti-emetic Usage

10.3.1 Measurement Definition

Post-operative Anti-emetic Usage is defined as the total amount of IV ondansetron administered to a patient during the first 48 hours post-operatively.

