1.2. Secondary Objectives

1.2.1 To determine if pre-operative TAP blocks with continued infusion of local anesthetic post-operatively affect post-operative pain scores as compared to a placebo TAP block.

1.2.2 To determine if pre-operative TAP blocks with continued infusion of local anesthetic post-operatively affect anti-emetic usage as compared to a placebo TAP block.

1.2.3 To determine if pre-operative TAP blocks with continued infusion of local anesthetic post-operatively affect time to ambulation post-operatively as compared to a placebo TAP block.

1.2.4 To determine if pre-operative TAP blocks with continued infusion of local anesthetic post-operatively affect time to first bowel movement as compared to a placebo TAP block.

1.2.5 To determine if pre-operative TAP blocks with continued infusion of local anesthetic post-operatively affect patient-reported quality of life as compared to a placebo TAP block.

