4.2 Hospitalization for reconstructive surgery

4.2.1 TAP Catheter Placement and Dosing:

On the day of surgery, bilateral TAP catheters will be placed using ultrasound guidance by the anesthesiologist in the pre-operative staging area prior to entering the operating room. Patients in the experimental group will receive an infusion of 0.125% bupivacaine and patients in the control group will receive an infusion of saline. Both groups will receive the following dosing:

- Initial bolus of 15mL pre-operatively
- 10mL bolus q4h intraoperatively with an option of 1-2mL per hour basal rate
- 10mL bolus q4h post-operatively with an option of 1-2mL per hour basal rate

TAP catheters will be discontinued on post-operative day (POD) 2, and the time will be recorded.

4.2.2 Post-Operative Pain Medication Regimen:

All patients will be provided with a patient controlled analgesia (PCA) infusion post-operatively providing IV hydromorphone. The PCA will be discontinued on POD2. Other pain medications available immediately after leaving the operating room will include the following:

- Acetaminophen IV or PO around the clock, per physician preference
- IV hydromorphone (dilaudid) 0.5 mg every 4 hours as needed for breakthrough pain, with an option to titrate up dose or frequency, per physician preference
- PO oxycodone 5-10 mg every 3 hours as needed for pain, with an option to titrate up dose or frequency, per physician preference
- Any pre-operative medications may be continued

4.2.3 Post-Operative Anti-Emetic Medication Regimen:

All patients will have available IV ondansetron (zofran) 4 mg every 4 hours as needed for nausea. Patients unable to take ondansetron will be given metocloprmiade (reglan).

4.2.4 Post-Operative Measurements:

Patients will be asked to rate their pain level on the Visual Analog Scale (VAS) every 4 hours while hospitalized unless they are sleeping. The total dosage of IV hydromorphone administered (via both the PCA and the as needed medications for breakthrough pain) will be recorded in 8-hour periods (midnight to 8am, 8am to 4pm, 4pm to midnight). The use of other pain medications, as well as anti-emetic medications, will be recorded in the same 8-hour periods. Time to ambulation, time to first bowel movement after surgery, and time to discharge will be recorded.

4.2.5 Evaluation for Discharge:

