10.3.2 Measurement Methods

Post-operative Anti-emetic Usage will be determined by examining the patient's chart and medication administration history.

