12.5.2 Post-operative Anti-emetic Usage

12.5.2.1 Analysis Population

Subjects will be grouped by study intervention, with experimental subjects being compared to control subjects. Missing data will be dropped, and subjects who were non-adherent to the protocol will be excluded.

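### The anti-emetic outcome counts only IV ondansetron, so patients whom the protocol gives metoclopramide are under-counted and the arm difference is diluted

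*Combined protocol and SAP*

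**What the plan says.** Objective 1.2.2 asks whether the block with continued infusion will "affect anti-emetic usage as compared to a placebo TAP block". It names no drug.

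Section 4.2.3 sets out the regimen: "All patients will have available IV ondansetron (zofran) 4 mg every 4 hours as needed for nausea". The next sentence covers the exception: "Patients unable to take ondansetron will be given metocloprmiade (reglan".

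Section 10.3.1 then narrows the outcome to one drug: "the total amount of IV ondansetron administered to a patient during the first 48 hours post-operatively". Section 10.3.2 names the data source (the chart and the medication administration history) and 10.3.3 repeats the 48-hour window.

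On data capture, section 4.2.4 is broader than 10.3.1: "The use of other pain medications, as well as anti-emetic medications, will be recorded in the same 8-hour periods".

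For the analysis, 12.5.2.1 says: "Missing data will be dropped, and subjects who were non-adherent to the protocol will be excluded". Section 12.5.2.2 specifies an analysis of covariance adjusted for the stratification variables. Neither section has a rule for patients given metoclopramide.

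**The concern.** The outcome is titled and motivated as anti-emetic use, but its definition measures exposure to one of the two anti-emetics in the protocol. A nauseated patient treated only with metoclopramide gets the same value, 0, as a patient who was never nauseated. A patient who changes drug keeps only the ondansetron given before the change. This is a stated scoring rule that returns the wrong value for identifiable patients, not a missing detail.

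At stake is one secondary comparison. Patients wrongly scored as zero dilute any true difference in anti-emetic use, and they may also add variance. The result would still be reported under the name of anti-emetic usage.

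**Working it through.** **1. Can another part of the plan repair the score?**

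- Missing-data rule (12.5.2.1): no. The zero is a recorded value, not a missing one.
- Exclusion for non-adherence (12.5.2.1): no. Section 4.2.3 itself directs these patients to metoclopramide, so they are following the protocol.
- Covariance adjustment (12.5.2.2): no. It adjusts for stratification variables, not for which drug was given.
- Extreme-value sensitivity analyses (12.4.1): no. They belong to the primary outcome and address missing data.

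**2. The plan's own figure.** Section 12.6.2 has SD 20 mg, difference 10 mg, 80% power, two-tailed t-test and 64 per arm. No alpha is stated, so I assume 0.05. Then n = 2 × (1.960 + 0.842)² × 20² / 10² = 62.8, or 63 per arm. The t-test power at 64 per arm is 80.1%, so the figure reproduces. It concerns the primary outcome only. The plan gives no mean, SD, effect or power for anti-emetic use.

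**3. Effect of one patient.** At 4 mg every 4 hours, 48 hours allow 48 / 4 = 12 doses, or 48 mg. With 64 per arm, a patient who needed 4 doses (16 mg) and is scored 0 lowers the arm mean by 16 / 64 = 0.25 mg. One who needed all 12 lowers it by 48 / 64 = 0.75 mg.

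**4. Equal shares in both arms.** Let a random share f of each arm be scored 0, with true arm mean μ and SD 1. The recorded mean is (1 − f)μ and the variance is (1 − f)(1 + μ²) − ((1 − f)μ)². The expected difference is therefore (1 − f) times the true one.

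Assumptions for illustration: true difference 0.5 SD, control mean 1 to 2 SD, 64 per arm, two-sided 5%, normal approximation. Worked case with f = 10% and control mean 1:

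- difference = 0.9 × 0.5 = 0.45
- control variance = 0.9 × 2 − 0.81 = 0.99
- experimental variance = 0.9 × 1.25 − 0.2025 = 0.9225
- SE = √((0.99 + 0.9225) / 64) = 0.173
- ratio = 0.45 / 0.173 = 2.60, giving power 74%

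| f (both arms) | Expected difference (SD) | Power, control mean 1 SD | Power, control mean 2 SD | Type I error |
|---|---|---|---|---|
| 0% | 0.50 | 81% | 81% | 5% |
| 2% | 0.49 | 79% | 78% | 5% |
| 5% | 0.475 | 77% | 73% | 5% |
| 10% | 0.45 | 74% | 65% | 5% |
| 20% | 0.40 | 66% | 51% | 5% |

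**5. A second assumed model.** Simulated dose counts (negative binomial, size 1.5, means 4.5 and 3.0 doses, 64 per arm) give power of about 64% with no mis-scoring, 63% at f = 1–2%, 60% at 5%, 55% at 10% and 46% at 20%. About 5.5% of simulated control patients exceed the 12-dose limit of step 3. Capping at 12 gives about 62% at baseline and 58%, 53% and 45% at 5%, 10% and 20%. The pattern is the same. With equal true means and equal shares, the rejection rate stays at about 5%.

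**6. Unequal shares.** Suppose 5% of the experimental arm and 15% of the control arm were scored 0. Under the model of step 4, a true 0.5 SD benefit shrinks to 0.28–0.38 SD. With no true effect, a false difference of 0.10–0.20 SD against the block appears and is declared significant in 9–17% of trials. Nothing in the documents indicates such an imbalance; these shares are chosen only to show the mechanism.

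**The case against.** The strongest reply is that metoclopramide is an exception, not a free second choice. Section 4.2.3 reserves it for patients who cannot take ondansetron. If few patients are in that position, almost nothing changes: at 1–2% the loss is at most about three points of power in either model. This stands. The documents give no share, so a material loss cannot be asserted.

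A reader might also infer that the definition biases the comparison in either direction and so could create a false finding. The documents do not support that. If inability to take ondansetron predates randomization, it is balanced between the arms in expectation. Section 3.4 blinds the anesthetist, surgeon, nurses and coordinators. The consequence is then dilution toward no difference, with type I error intact. Chance imbalance in the number of metoclopramide patients is sampling noise, which the standard error already reflects; it is not bias. A systematic false difference needs shares that diverge by arm after randomization.

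Finally, the choice of replacement is partly a matter of judgement. Any use (yes or no), or the ondansetron total with a stated rule for metoclopramide patients, would also close the gap. That is fair, but it is not a reason to leave the definition as it is.

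**Conclusion.** The mismatch is established from the text and does not depend on any assumed figure: 10.3.1 does not measure what objective 1.2.2 asks, given the regimen in 4.2.3, and no other section corrects it.

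The consequence is conditional. With equal shares f scored as zero, unrelated to how much anti-emetic a patient needs, the estimated difference falls to (1 − f) of the true one and power drops. The effect may be negligible (f of 1–2%) or material (f of 10–20%). All power figures rest on assumed effects, distributions and shares. A spurious difference remains possible only if the shares differ by arm after randomization, which the documents neither describe nor exclude.

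One secondary outcome is affected. The primary outcome, its analysis and the sample size are not.

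**What to change.** Redefine the outcome in 10.3.1 as the number of administrations of any anti-emetic agent in the first 48 hours after surgery, analysed as in 12.5.2.2. Keep total IV ondansetron in mg over the same window as a supportive analysis.

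The cost is one changed sentence and one added line, preferably before unblinding. No new data are needed: 4.2.4 already records anti-emetic medications without restriction to one drug, and the medication administration history named in 10.3.2 supplies the count. Patient care does not change. The small downside is that one administration of either drug counts the same and dose size is ignored; the supportive analysis keeps the dose information for ondansetron.

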10.3.2 Measurement Methods

Post-operative Anti-emetic Usage will be determined by examining the patient's chart and medication administration history.

10.3.3 Measurement Time Points

Post-operative Anti-emetic Usage will be examined during the first 48 hours post-operatively.

10.4 Secondary Outcome Measure: Time to Ambulation

10.4.1 Measurement Definition

Time to Ambulation is defined as the time to the first instance a patient is able to stand up and walk a few steps post-operatively.

10.4.2 Measurement Methods

The time of first ambulation will be recorded by the nurse on shift. Time to Ambulation will be calculated from midnight on POD 1.

10.5 Secondary Outcome Measure: Time to First Bowel Movement

10.5.1 Measurement Definition

Time to First Bowel Movement is defined as the time to the first instance a patient passes stool post-operatively.

10.5.2 Measurement Methods

The time of first bowel movement will be recorded by the nurse on shift. Time to First Bowel Movement will be calculated from midnight on POD 1.

10.6 Secondary Outcome Measure: Quality of Life

10.6.1 Measurement Definition

Quality of Life is defined as the calculated score from the BREAST-Q questionnaire.¹⁹

10.6.2 Measurement Methods

Quality of Life will be measured by having the patient fill out the BREAST-Q questionnaire pre-operatively, as well as post-operatively between 1-6 months after surgery.

10.6.3 Measurement Time Points

Quality of Life will be measured 1-6 months after surgery.

11. REGULATORY CONSIDERATIONS

11.1 Institutional Review of Protocol

The protocol, the proposed informed consent and all forms of participant information related to the study (e.g. advertisements used to recruit participants) will be reviewed and approved by the Stanford IRB and Stanford Cancer Institute Scientific Review Committee (SRC). Any changes made to the protocol will be submitted as a modification and will be approved by the IRB prior

to implementation. The Protocol Director will disseminate the protocol amendment information to all participating investigators.

